12. SAFETY ASSESSMENTS AND REPORTING

12.1 Adverse Event (AE)

An AE or adverse experience is:

Any untoward medical occurrence in a study participant administered a medicinal product, which does not necessarily have to have a causal relationship with this treatment (the study medication).

An AE can therefore be any unfavourable and unintended sign (including an abnormal laboratory finding), symptom or disease temporally associated with the use of the study medication, whether or not considered related to the study medication.

12.2 Adverse Reaction (AR)

Adverse reactions include all untoward and unintended responses to a medicinal product related to any dose.

The phrase "responses to a medicinal products" means that a causal relationship between a study medication and an AE is at least a reasonable possibility, i.e., the relationship cannot be ruled out.

All cases judged by either the reporting medically qualified professional or the sponsor as having a reasonable suspected causal relationship to the study medication qualify as adverse reactions.

12.3 Serious Adverse Event (SAE)

To ensure no confusion or misunderstanding of the difference between the terms "serious" and "severe", which are not synonymous, the following note of clarification is provided:

The term "severe" is often used to describe the intensity (severity) of a specific event (as in mild, moderate, or severe myocardial infarction); the event itself, however, may be of relatively minor medical significance (such as severe headache). This is not the same as "serious," which is based on patient/event outcome or action criteria usually associated with events that pose a threat to a participant's life or functioning. Seriousness (not severity) serves as a guide for defining regulatory reporting obligations.

A serious adverse event (SAE) or serious adverse reaction (SAR) is any untoward medical occurrence that at any dose:

- Results in death
- Is life-threatening

NOTE: The term "life-threatening" in the definition of "serious" refers to an event in which the participant was at risk of death at the time of the event; it does not refer to an event which hypothetically might have caused death if it were more severe

- Requires inpatient hospitalisation or prolongation of existing hospitalisation, except for routine hospitalization for *Plasmodium vivax* or *falciparum* malarial disease
- Results in persistent or significant disability/incapacity
- Is a congenital anomaly/birth defect

12.4 The difference between an SAE and an SAR is the relatedness attributed to the study treatment. An SAR has the same standard for determining causal relationship as outlined above in the section describing adverse reactions. Expected Serious Adverse Reactions

An expected serious adverse reaction (SAR) is a serious adverse reaction, the nature or severity of which is consistent with the applicable product information. Primaquine can cause significant haemolysis in G6PD deficient persons (<30% of normal G6PD activity or 2.25 IU/gHb by the quantitative G6PD spectrophotometric assay). Only individuals with 40% or greater G6PD activity (3.00 IU/gHb) will be enrolled in the study, therefore significant haemolysis is unlikely to occur.

If haematocrit is <30%, the participant will receive the standard anemia treatment (ferrous sulphate 200 mg twice daily, folic acid 5 mg daily, vitamin B12 100 mg twice daily and Vitamin C 100 mg twice daily) until the haematocrit rises above 30%. If the fractional drop in haematocrit is >25%, an adverse event sheet will be completed and the patient will be followed as clinically indicated. Methemoglobin levels increase in normal persons taking primaquine but are usually asymptomatic. Symptoms may consist of cyanosis, lethargy or dyspnea. During study drug administration, symptoms of methemoglobinemia and methemoglobin levels (using a Masimo Radical 57 oximetry machine) will be monitored. If a participant develops an increase in SpMet (3-20%) and does not have symptoms, the study medication will be continued and the participant will be monitored until levels normalize. If a participant develops symptomatic methemoglobinemia or if SpMet >20%, the study medication will be stopped, patient admitted and treated with ascorbic acid.

12.5 Suspected Unexpected Serious Adverse Reactions

A serious adverse reaction, the nature or severity of which is not consistent with the applicable product information.

12.5.1 Management of SAR

We do not expect to see subjects with profound falls in haemoglobin because all subjects will have a normal G6PD phenotype. However, as a safety net, individual subject stopping criteria are in place (see section 9.7). If a subject requires a blood transfusion, they will be managed by the research team. Subjects will be referred to Mae Sot General Hospital for further management, if determined to be clinically unstable.

The clinical indications for a blood transfusion are:

- Haemoglobin <6 g/dL or Haematocrit <18%, or
- Clinically significant symptoms & signs of anaemia (e.g. dizziness, feeling tired, difficulty breathing, pallor or low blood pressure).

12.6 Reporting Procedures for All Adverse Events

All AEs occurring during the study observed by the investigator or reported by the participant, whether or not attributed to study medication, will be recorded on the CRF up to day 21.

The following information will be recorded: description, date of onset and end date, severity, assessment of relatedness to study medication, other suspect drug or device and action taken. Follow-up information should be provided as necessary.

AEs considered related to the study medication as judged by a medically qualified investigator or the sponsor will be followed until resolution or the event is considered stable. All AEs will be managed by the clinical study site team in accordance with good medical practices and the standard clinical practices in place at the hospital. The clinical team will assess and treat or refer the participating child for medical care as appropriate, which may include additional study visits, if necessary. All related AEs that result in a participant's withdrawal from the study or are present at the end of the study, should be followed up until a satisfactory resolution occurs.

It will be left to the investigator's clinical judgment whether or not an AE is of sufficient severity to require the participant's removal from treatment (see Section 6.4). A participant may also voluntarily withdraw from treatment due to what he or she perceives as an intolerable AE. If either of these occurs, the participant will be given appropriate care under medical supervision until symptoms cease or the condition becomes stable.

The severity of events will be assessed on the following scale:

- 1 = mild (asymptomatic or mild symptoms requiring clinical or diagnostic observations only; no intervention indicated)
- 2 = moderate (symptoms limit age appropriate instrumental activities of daily living; minimal, local or non-invasive intervention indicated)

- 3 = severe (symptoms are medically significant but not life threatening, disabling, or limit self care activities of daily living; hospitalization or prolongation of hospitalization indicated)
- 4 = life threatening (symptoms are life threatening; urgent intervention indicated)
- 5 = death

A medically qualified investigator will assess the relationship of AEs to the study medication. The relatedness of AEs to the study product administration will be assessed on the following scale:

- Definitely related: adverse event and administration of study product are related in time, and a direct association can be demonstrated with the study product
- Probably related: adverse event and administration of study product are reasonably related in time, and the adverse event is more likely explained by the study product than by other causes
- Probably not related: a potential relationship between administration of study product and adverse event could exist, but is unlikely, and the adverse event is most likely explained by causes other than the study product
- Not related: the adverse event is clearly explained by another cause unrelated to administration of the study product. Reportable events must have documentation to support the determination of “not related”

Any pregnancy occurring during the clinical study and the outcome of the pregnancy will be recorded and followed up for congenital abnormality or birth defect.

12.7 Reporting Procedures for Serious Adverse Events

All serious adverse events will be reported to the PI and sponsor within 1 working day and to the Ethics Committee as required. SAEs will be reported to the Data Safety Monitoring Board as part of interim or final reports. SARs, whether expected or unexpected, will be reported to the DSMB within 72 hours of the PI and sponsor's notification.

12.8 Study Halting Rules

Administration of study drug will be halted if severe haemolysis (defined as absolute haemoglobin reduction of 3.0 g/dL or absolute haemoglobin below 7.0 g/dL or any significant signs or symptoms of haemolysis such as difficulty breathing or low blood pressure) occurs at the following frequencies among study participants:

- Heterozygous women
 - 3/12 individuals in Arm 1A meeting criteria of severe haemolysis
 - 3/12 individuals in Arm 1B meeting criteria of severe haemolysis
- Wildtype men/women
 - 6/48 individuals total from either Arm 1A or 1B meeting criteria of severe haemolysis

The PI will notify the study sponsor and co-investigators immediately when the threshold in any of the above groups of participants is met for severe haemolysis and enrollment screens will stop accepting new study participants. Prior to study initiation, the DSMB will identify and approve any additional study halting rules to be followed for the study. When any event occurs that meets a study halting rule, the study sponsor will inform the DSMB members within 24 hours of notification and will provide the DSMB with AE listing reports. The DSMB will convene an ad hoc meeting by teleconference or in writing as soon as possible.

The objective of the safety review is to decide whether the study (or study drug for an individual or study cohort) should continue per protocol, proceed with caution, be further investigated, be discontinued, or be modified and then proceed. Suspension of enrolment (for a particular group or for the entire study) is a potential outcome of a safety review. The DSMB will provide its recommendations to the study sponsor. The study sponsor will inform the IRBs/IECs of the temporary halt and the disposition of the study.

12.9 Safety Oversight (Data Safety Monitoring Board)

Safety oversight will be under the direction of a Data Safety Monitoring Board (DSMB), an independent group of experts that advises the study investigators. The DSMB will be composed of at least three voting members, including at least one malaria expert and one biostatistician. One of the DSMB members must be a clinician. The primary responsibilities of the DSMB are to 1) periodically review and evaluate the accumulated study data for participant safety and study conduct and progress, and 2) make recommendations concerning the continuation, modification, or termination of the study. The DSMB will operate under the rules of an approved charter that will be reviewed at the organizational meeting of the DSMB held before the study begins recruitment. At this time, each data element that the DSMB needs to assess and the roles and responsibilities of DSMB members will be clearly defined.

The DSMB will meet once approximately half of the target sample size has been enrolled or three months after recruitment begins, whichever is sooner, and then again at the end of the study to assess safety data by randomization arm. Prior to each DSMB meeting, a study report will be distributed to the DSMB for review. Adverse events will be presented in aggregate summary, whereas any SAEs will be presented individually in DSMB reports. DSMB findings will be reported to the PI and sponsor within a reasonable amount of time specified in the approved charter.

13. DATA HANDLING AND RECORD KEEPING

13.1 Data Collection

All study data will be recorded on standard paper Case Report Forms (CRFs). Data will be entered on a secure database in accordance with standard operating procedures (SOPs).

Source documents are original documents, data, and records from which participants' CRF data are obtained. These include, but are not limited to, hospital records (from which medical history and previous and concurrent medication may be summarized into the CRF), clinical charts, laboratory, correspondence, log books, and CRFs. For most variables, the CRF will be considered the source document.

All documents will be stored safely in confidential conditions. On all study-specific documents, other than the signed consent and screening logbook, the participant will be referred to by the study participant number/code, not by name.

13.2 Data Access

The participants will be identified by a study identification number and the patient (clinical) identification number in the SMRU clinical database. The name and any other identifying detail will NOT be included in any study data electronic file. The database linking the volunteer's clinical identification number to the study identification number will be kept by the staff at SMRU and PATH will not have access to the link. All records will be kept locked and all databases will be password protected such that clinic staff and study staff will have access to their respective databases.

Direct access will be granted to authorized representatives from the sponsor, host institutions and the regulatory authorities to permit trial-related monitoring, audits and inspections.

13.3 Data Storage

SMRU will maintain, and store securely, complete, accurate and current study records throughout the study. In accordance with regulations, study staff will retain all study records on site for at least five years after study closure. Study records will not be destroyed prior to receiving approval for record destruction from the sponsor. No study records will be destroyed while study specimens are still being stored. Applicable records include source documents, site registration documents and reports, informed consent forms, and notations of all contacts with participants.

13.4 Quality Control and Quality Assurance

The study will be conducted in accordance with the current approved protocol, International Conference on Harmonisation (ICH) good clinical practices (GCP), relevant regulations and standard operating procedures.

Regular monitoring will be performed according to ICH GCP. A SMRU data monitoring team visits each clinical site roughly once per month to review completion of consent forms, CRFs, and study file management. The monitor collects all study-related forms and brings them to the SMRU offices for database entry and storage. Data will be evaluated for compliance with the protocol and accuracy in relation to source documents. Study data will be aggregated into a database and an electronic monitoring report will be generated every month summarizing key indicators for study compliance. These indicators include but are not limited to the number of participants consented, the number of samples acquired, any deviations from study procedures, and corrective actions taken. Following written standard operating procedures, the monitors will verify that the clinical trial is conducted and data are generated, documented and reported in compliance with the protocol, GCP and the applicable regulatory requirements. In addition, a PATH representative will conduct site monitoring visits as needed to ensure compliance with the protocol and relevant SOPs.

14. STATISTICAL ANALYSIS

Primary aim: *To understand the risk of haemolysis in healthy G6PD heterozygous females receiving (i) primaquine for 14 days at 0.5 mg/Kg and (ii) chloroquine for 3 days and then primaquine for 14 days at 0.5 mg/Kg.*

This will be done by studying survival rates of RBC populations with known G6PD by method of flow cytometry which will measure the G6PD activity of a random selection of 10,000 RBCs throughout various time points in the study. Descriptive statistics will characterize the haematological markers collected, including absolute haemoglobin reduction from baseline on exposure to primaquine over treatment course as well as absolute reduction in haemoglobin-related change in intracellular G6PD concentration profiles over treatment course. Additional descriptive statistics characterizing haematocrit levels, absolute and fractional haematocrit reduction from baseline, and changes in intracellular G6PD concentration populations over time (as measured by flow cytometry) will be determined for each study group in each treatment arm. Estimates of lysis from haematocrit levels and from flow cytometry will be checked for concordance.

Correlations among these exposure metrics between arms will be evaluated. Normality of measurements will be assessed and non-parametric tests or log transformations will be used as appropriate.

Secondary aims: (1) *To determine if additional haematologic measures are critical inputs or determinants for a drug-related haemolytic risk model, (2) to associate primaquine and chloroquine drug levels at the time of sampling with patient haematological and G6PD profiles, and (3) to measure frequency of adverse events in women heterozygous for G6PD treated with current standard of care for P. vivax malaria.*

Descriptive statistics characterizing dextromethorphan assay results, CBC, methemoglobin, reticulocyte count, and bilirubin and urine urobilinogen levels; drug levels of chloroquine and primaquine; and adverse events will be determined for each study group in each treatment arm. Correlations between haematology measures and drug levels at the time of sampling between arms will be evaluated. Normality of measurements will be assessed and non-parametric tests or log transformations will be used as appropriate.

A mixed affects regression model will be developed to understand the dynamic relationship between predictors such as collected haematological markers, gender, gross G6PD activity, G6PD zygosity, Dextromethorphan assay results, PQ concentration, bilirubin levels and their effect on a patient's absolute drop in haemoglobin and haematocrit.

A mixed affects regression model will be developed to understand the dynamic relationship between predictors such as collected haematological markers, gender, gross G6PD activity, G6PD zygosity, Dextromethorphan results, PQ concentration, bilirubin levels and their effect on the drop in the number of cells within specified bins of G6PD activity measured by G6PD cytometry assay.

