10.1 G6PD Assays

- **Quantitative G6PD spectrophotometric test** (30µl from blood taken from CBC)

The quantitative spectrophotometric assessment of G6PD activity in blood is based on the measure of the increase in absorbance at 340nm due to the production of NADPH during incubation of haemolyzed blood with G6P and NADP- substrates. Available commercial kits will be used for this test. Quantitative G6PD enzyme activity will be assessed on every blood draw as per study design. The quantitative G6PD spectrophotometric test will be performed as part of screening procedures. 100% normal G6PD activity for this population using this assay in this laboratory has been determined previously to be 7.51 IU/gHb (38). The 40% normal activity threshold used for inclusion is therefore 3.00 IU/gHb.

- **G6PD flow cytometry** (100µl from blood taken from CBC)

Whole blood specimens will be characterized for intracellular G6PD activity by flow cytometry as described previously Shah et al. 2012. Specimens will be analyzed using an Accuri™ C6-UV flow-cytometer (BD Biosciences); 10,000 events will be recorded in the FL1 channel 533 +/- 30 nm.

G6PD flow cytometry testing will be assessed on every blood draw as per study design.

The cytofluorometric data analysis tool (already developed by PATH and validated with SMRU) will be further refined to improve assessment in changes of red blood cell distribution. This will be refined to include a model that describes how sub populations of red blood cells express and change in G6PD activity in time due to treatment with primaquine.

- **G6PD fluorescent spot test** (50µl from blood taken from CBC)

Most field deployable G6PD tests are qualitative and the standard of care for case management is the G6PD fluorescent spot test (FST). The G6PD FST will be performed on recruitment as a comparator to the quantitative test. An EDTA tube will be used to acquire blood for glucose-6-phosphate dehydrogenase semi-quantitative fluorescent spot test for initial screening in the field. The fluorescent spot test (R&D Diagnostics) will be performed as per manufacturer's instructions. Additional qualitative tests such as the CareStart G6PD test may be performed depending on availability.

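### As written, the second mixed model's drop in cells per G6PD bin is a change in share of a fixed 10,000-cell read, so it understates loss while total red cells are below baseline

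*Combined protocol and SAP*

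**What the plan says.** Section 10.1 (G6PD flow cytometry) fixes the read for each specimen: "10,000 events will be recorded in the FL1 channel". It also states that "G6PD flow cytometry testing will be assessed on every blood draw as per study design", using blood taken for the CBC.

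Section 14, primary aim, describes the cytometry analysis in terms of survival: "This will be done by studying survival rates of RBC populations with known G6PD" and then "by method of flow cytometry which will measure the G6PD activity of a random selection of 10,000 RBCs". It adds a cross-check: "Estimates of lysis from haematocrit levels and from flow cytometry will be checked for concordance". On scale, it says only that "non-parametric tests or log transformations will be used as appropriate".

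The second mixed model at the end of section 14 lists haematological markers, gross G6PD activity and other predictors, and models "their effect on the drop in the number of cells within specified bins of G6PD activity measured by G6PD cytometry assay".

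Two places might hint at a link to total red cells. The second primary endpoint (section 7.2.1) calls the change in the G6PD profile *haemoglobin-related*, without a formula. Section 10.1 says that the cytometry analysis tool "will be further refined to improve assessment in changes of red blood cell distribution". Neither says that bin counts will be scaled by red-cell count, haematocrit or haemoglobin.

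**The concern.** A read of fixed size shows how the sampled cells divide among bins. It does not show how many cells per microlitre remain. If a woman loses red cells, the cytometer still collects 10,000, and the surviving cells fill the places of the lost ones. A bin that lost cells then shows too small a drop, and a bin that lost none shows a gain.

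This touches the second mixed model and the cytometry survival summaries under the primary aim. Bin changes would mix true loss with each woman's fall in total red cells, so women and days with different falls would not be comparable. Section 6.2 notes that the balance of the two cell populations varies widely between heterozygous women. On an untransformed scale the distortion can therefore follow the low-G6PD share, and with it gross G6PD activity, one of the model's predictors. The error would pass into the risk model that the pilot is meant to inform.

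**Working it through.** The plan gives no numerical figure for this model, so there is none to reproduce. The check is algebra.

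**Inputs**
- Read size E = 10,000 (sections 10.1 and 14).
- T = total red cells relative to baseline. The documents give no expected value. For illustration, T = 0.90 borrows the 10% difference in means in section 8.4 (read as relative), and T = 0.75 borrows the 25% haematocrit figure in section 12.4. Neither is an expected fall. Using haematocrit as a proxy assumes unchanged cell volume.
- L = true net loss in a bin; p = baseline share of low-G6PD cells. Neither is given, so both are assumed.

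**Identity**
- The count in bin b at time t is E × N_b(t) / N_total(t).
- Recorded ratio to baseline = true ratio / T, so recorded loss = 1 − (1 − L)/T.
- An unchanged bin reads as a gain of 1/T − 1.
- A uniform loss has 1 − L = T and reads as zero.

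**Readings**
- T = 0.90, L = 20%: 1 − 0.80/0.90 = 11.1%. An unchanged bin gains 1/0.90 − 1 = 11.1%.
- T = 0.75, L = 50%: 1 − 0.50/0.75 = 33.3%. A uniform 25% loss reads 0.
- T = 1.00, L = 20%: 20%.
- T = 1.02, L = 20%: 1 − 0.80/1.02 = 21.6%.

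In counts, with p = 0.5, T = 0.75 and loss only in low-G6PD cells, the low bin goes from 5,000 to 3,333 and the high bin from 5,000 to 6,667. Multiplying by T gives 2,500 and 5,000, the true position. The gap of 833 events (3,333 − 2,500) compares with a counting standard error of √(10,000 × 0.25) = 50 per read, or about 71 for a difference.

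**Dependence on share and replacement**

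Let a fraction r of lost cells be replaced in normal bins, so T = 1 − pL(1 − r). Recorded loss for a true loss of 20%:

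| Low-G6PD share | r = 0 | r = 0.5 | r = 1 |
|---|---|---|---|
| 20% | 16.7% | 18.4% | 20% |
| 40% | 13.0% | 16.7% | 20% |
| 60% | 9.1% | 14.9% | 20% |

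These shares match the 80% to 40% activity range in section 8.3.1 if low-G6PD cells have almost no activity. If they keep 20% of normal activity, the shares are 25% to 75% and the r = 0 readings are 15.8% to 5.9%.

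**What rescaling does elsewhere**
- Σ(share × RBC) = RBC. The rescaled total is the red-cell count itself.
- log(share × RBC) = log share + log RBC. If log RBC is also a predictor, its coefficient rises by exactly 1 and the others do not change. One simulated data set gave 0.354 and 1.354, with the activity coefficient −0.219 both times.

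**The case against.** Several points on the other side stand in part.

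*A later step may be intended.* The survival wording, the planned flow-based estimates of lysis, the undefined haemoglobin term and an existing analysis tool all leave room for one. A reader might infer that the investigators will certainly analyse raw counts; the documents do not support that. They show only that no scaling is stated.

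*Shares can yield lysis without T.* If high-G6PD cells are stable and none are replaced, the low/high odds recover the true loss: 3,333/6,667 = 0.5 against 1 at baseline is a 50% loss. Replacement breaks this. With p = 0.4, L = 20% and half replacement, the odds go from 0.40/0.60 = 0.667 to 0.32/0.64 = 0.50, a reading of 25%. The data are therefore not inherently understated; the stated outcome is.

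*A log model could repair the coefficients.* With log red-cell count among the predictors, the other coefficients match those for the rescaled outcome. The plan does not specify that model, and the match fails on an untransformed scale.

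*The concordance check would catch it.* It might expose a mismatch, but it corrects nothing. Rescaling inside that check would also defeat it, because haematocrit comes from the same CBC blood (Table 3 footnote).

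*Rescaling has its own errors.* This is true. Shares ignore blood draws and plasma-volume change, because both affect every bin alike. The rescaled outcome records them as loss.

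*It is a pilot.* Section 8.4 says the haemolysis analyses are mainly descriptive. That limits the severity, but a bias in what is passed to the risk model does not average out.

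**Conclusion.** The point holds for the outcome as written. It is a change in share, and it understates net bin loss whenever total red cells are below baseline. This follows from the fixed read and needs no assumption about share or replacement. The size does rest on assumed values: 20% reads 11.1% at T = 0.90, and 50% reads 33.3% at T = 0.75.

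Three stronger readings are not supported. Loss is not always understated: the bias vanishes at T = 1, reverses above it, and can change over Days 1 to 21 as cells are replaced. The borrowed 10% and 25% falls are not predictions. The absolute haemoglobin endpoint and the first mixed model do not use bin counts and are not affected.

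This should be fixed before analysis. It does not undermine the trial, since the data needed for the correction are already to be collected.

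**What to change.** - **Outcome.** In the second mixed model and the cytometry survival summaries, use bin share × red-cell count from the CBC of the same draw, relative to Day 1 pre-dose. Equivalently, model log bin count with minus log red-cell count as an offset, its coefficient fixed.
- **Name.** Call it net change in cell concentration per bin, not survival, because new cells and movement between bins also change it. Report the raw share change and reticulocytes beside it.
- **Predictors.** Do not enter same-draw red-cell count, haematocrit or haemoglobin as predictors of the rescaled outcome without noting the built-in coupling.
- **Concordance check.** Keep the rescaled total out of it. Use a share-based estimate of lysis, such as the change in low/high odds, and state that it equals true loss only with stable high-G6PD cells and no replacement.
- **Endpoint wording.** Define *haemoglobin-related* in the second primary endpoint consistently, with a formula.

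**Cost.** No new sample or assay is needed: cytometry uses CBC blood at every draw. Three downsides should be disclosed.
- The red-cell count adds measurement error (assumed CV 1–3%). Setting the bias against the added error, break-even is at a fall of 1 − 1/(1 + √2 × CV/√n): 1.4% to 4.1% for one woman and 0.4% to 1.2% for a mean of 12. At a 40% share and L = 20%, total error for one woman goes from 7.1 to 1.9–3.7 points with no replacement, but rises from 1.5 to 1.9–3.7 with full replacement.
- The scheduled draws lower the rescaled outcome. Table 4 gives 2 + 11 × 10 = 112 ml, which is 2.8% to 3.7% of an assumed 4 to 3 litres of blood before replacement. That is large enough to matter near the break-even falls, whose calculation leaves it out.
- Plasma-volume change moves the rescaled outcome but not the shares, which is a further reason to report both.
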